## List of abbreviations

AE	Adverse event
AUC	Area under the drug plasma (serum/blood) concentration-time curve
BSC	Best supportive care
Cmax	Maximal drug blood concentration
CRO	Contract research organization
CTCAE	Common Terminology Criteria for Adverse Event
DDI	Drug-drug interaction
DS&E	Drug Safety and Epidemiology
eCRF	Electronic case report form
EDC	Electronic data capture
FAS	Full analysis set
IB	Investigator's Brochure
ICF	Informed consent form
ICH	International Conference on Harmonization
IEC	Independent ethics committee
IIT	Investigator initiated trial
IN	Investigator notification
IRB	Institutional review board
mTOR	mammalian target of rapamycin
NET	Neuroendocrine tumors
PgP	P-glycoprotein
PHI	Protected health information
PI	Principal investigator
pNET	Pancreatic neuroendocrine tumors
RAD001	Everolimus
REB	Research ethics board
RECIST	Response evaluation Criteria in Solid Tumors
SAE	Serious adverse event
SEGA	Subependymal giant cell astrocytoma
Tmax	Time to reach the maximum drug blood concentration following drug administration
TSC	Tuberous sclerosis complex
VEGF	Vascular endothelial growth factor

## Glossary of terms

Assessment	A procedure used to generate data required by the study
Control drug	A study treatment used as a comparator to reduce assessment bias, preserve blinding of investigational drug, assess internal study validity, and/or evaluate comparative effects of the investigational drug
Cycles	Number and timing or recommended repetitions of therapy are usually expressed as number of days (e.g.: every 28 days)
Dose level	The dose of drug given to the patient (total daily dose)
Enrollment	Point/time of patient entry into the study; the point at which informed consent must be obtained (i.e. prior to starting any of the procedures described in the protocol)
Investigational treatment	Drug whose properties are being tested in the study. This also includes approved drugs used outside of their indication/approved dosage, or that are tested in a fixed combination. Investigational treatment generally does not include other study treatments administered as concomitant background therapy required or allowed by the protocol when used in within approved indication/dosage
Other study treatment	Any drug administered to the patient as part of the required study procedures that was not included in the investigational treatment
Patient Number (Patient No.)	A unique identifying number assigned to each patient/subject/healthy volunteer who enrolls in the study
Roll-over study	A roll-over study allows patients from multiple parent studies spanning multiple indications to continue to be treated within one study after the completion of the parent study(ies)
Study treatment	Includes any drug or combination of drugs in any study arm administered to the patient (subject) as part of the required study procedures, including placebo and active drug run-ins. In specific examples, it is important to judge investigational treatment component relationship relative to a study treatment combination; study treatment in this case refers to the investigational and non-investigational treatments in combination.

## **Amendment 01 (30-Aug-2016)**

### **Amendment rationale**

The amendment provides latest guideline of follow up toxicities such as evaluations for hepatic toxicities and work-up guidelines for potential Drug Induced Liver Injury (DILI) cases. In addition, this amendment has been implemented to provide updated information as well as clarification of sections of the protocol where additional guidance was required.

### **Changes to the protocol**

Section 1.2.1.2: Clinical experience language updated

Section 5.3: Updated contraception language based on new guidelines on pregnancy prevention.

Section 6.1: Definition of study treatment clarified. Relevant sections were also updated.

Section 6.3.2.1: New section added for drug-induced liver toxicity language.

Section 6.4: Added reference to IB for use concomitant medications.

Table 6-2: Updated inducers, and inhibitors of isoenzyme CYP3A based on IB update.

Table 6-3: Updated substrates, inducers, inhibitors of PgP and PgP/CYP3A dual inhibitors based on IB update.

Section 6.4.2: Updated vaccination language based on IB update.

Section 7.1.4.1: Section name updated in addition to adding new language.

Section 7.1.5: Section name updated.

Section 7.1.6: Added Lost to follow up language.

Section 7.2.2: Updated pregnancy testing language.

### **IRB/IEC**

A copy of this amended protocol will be sent to the Institutional Review Board (IRBs)/Independent Ethics Committee (IECs) and Health Authorities.

The changes described in this amended protocol require IRB/IEC approval prior to implementation.

**Protocol summary:**

Protocol number	CRAD001C1X01B
Title	An open label, multi-center everolimus roll-over protocol for patients who have completed a previous Novartis-sponsored everolimus study and are judged by the investigator to benefit from continued everolimus treatment.
Brief title	Study to collect and assess long-term safety of everolimus in patients who are on everolimus treatment in a Novartis-sponsored study and are benefiting from the treatment as judged by the investigator.
Sponsor and Clinical Phase	Novartis, II
Study type	Interventional
Purpose and rationale	The purpose of this study is to collect and assess long-term safety of everolimus in patients who are on everolimus treatment in a Novartis-sponsored study and are benefiting from the treatment as judged by the investigator.
Primary Objective(s) and Key Secondary Objective	To collect and assess long-term safety of everolimus of patients receiving everolimus in a Novartis-sponsored study which has reached its objectives and who are benefiting from treatment with everolimus.
Secondary Objectives	Not applicable
Study design	
This is a multi-center, open label study to collect and assess long-term safety of everolimus in patients being treated in current Novartis-sponsored studies and who are benefiting from treatment with everolimus judged by the investigator. There will be no screening period for this study. Eligible patients are to be consented and can start their treatment with everolimus as soon as they enter the study.
 
At least, patients must return to the study center on a yearly basis (<math>\pm</math> 3 months), but for resupply of study medication, the frequency of the receipt and dispensing must follow local practice (e.g., every 2 to 3 months). At this time the dose of everolimus is based on the investigator's judgment.
 
Adverse events (AEs) will be collected continuously throughout the study. For the safe and effective use of everolimus, patient may return to the clinic at any given time following local practice. When AEs are observed, additional visits will be arranged by investigator's discretion.
 
Patients will continue to be treated until they are no longer benefiting from everolimus as defined in the parent protocol (disease progression), develop unacceptable toxicities, withdraw consent, are non-compliant to the protocol, the investigator feels it is no longer in the patient's best interest to continue everolimus therapy or the patient dies, whichever comes first.
 
A patient will reach the end of study when everolimus treatment is permanently discontinued and the end of treatment visit has been performed. All patients must be followed for AEs for 30 days after the last dose of everolimus.
 
The study is expected to remain open for 5 years or until such time that enrolled patients no longer need treatment with everolimus, whichever comes first.

Population	Male and female patients, who are currently enrolled in a Novartis-sponsored everolimus study, are benefiting from treatment with everolimus and have fulfilled all their requirements in the parent study.
Inclusion criteria	
Patient is currently enrolled in a Novartis- sponsored everolimus study, receiving everolimus and has fulfilled all their requirements in the parent study.
 
Patient is currently benefiting from the treatment with everolimus, as determined by the guidelines of the parent protocol.
 
Patient has demonstrated compliance, as assessed by the investigator, with the parent study protocol requirements.

Exclusion criteria	Patient has been permanently discontinued from everolimus study treatment in the parent study due any reason.
Investigational and reference therapy	Everolimus, 2.5 – 10 mg/day.
Efficacy assessments	Not applicable

Safety assessments	Reported AEs will be collected continuously throughout the study. For the safe and effective use of everolimus, medical monitoring should be performed as clinically indicated at the physician's discretion.
Other assessments	Not applicable
Data analysis	Statistical analysis will be performed when all patients discontinued the trial or the 30-day safety follow-up was completed, whichever comes earlier. Those analyses results will be used to document the summary of the safety. Data will be used only for descriptive summary of patients remaining on drug.
Key words	Everolimus, roll-over study

## 1 Background

### 1.1 Overview of disease pathogenesis, epidemiology and current treatment

The purpose of this study is to allow continued use of everolimus in patients who are currently receiving everolimus treatment in a Novartis-sponsored study that has reached its study objectives, are not progressing on the current study treatment as defined by the parent protocol and are unable to access everolimus treatment outside of a clinical study. The roll-over study is designed to accept patients with varied disease origins. Please refer to the parent protocol for the disease background information and rationale for use of everolimus in their individual indications. See also [Section 1.2.1.2](#).

### 1.2 Introduction to investigational treatment(s) and other study treatment(s)

#### 1.2.1 Overview of everolimus (RAD001)

Everolimus is a proliferation signal inhibitor in the mammalian target of rapamycin (mTOR) drug class. The mTOR pathway activity is modulated by the PI3K/AKT pathway, a pathway known to be dysregulated in numerous human cancers.

Everolimus is being investigated as an anticancer agent based on its potential to act

- directly on the tumor cells by inhibiting tumor cell growth and proliferation;
- indirectly by inhibiting angiogenesis leading to reduced tumor vascularity [via potent inhibition of tumor cell vascular endothelial growth factor (VEGF) production and VEGF-induced proliferation of endothelial cells].

At the cellular and molecular level, everolimus acts as a signal transduction inhibitor. It selectively inhibits mTOR, a key protein kinase which regulates cell growth, proliferation and survival. The mTOR kinase is mainly activated via the phosphatidylinositol 3-kinase (PI3-Kinase) pathway through AKT/PKB and the tuberous sclerosis complex (TSC). Mutations in these components or in phosphatase and tensin homolog, a negative regulator of PI3-kinase, may result in their dysregulation. Abnormal functioning of various components of the signaling pathways contributes to the pathophysiology of numerous human cancers. Various preclinical models have confirmed the role of this pathway in tumor development ([Cohen et al 2005](#)).

The main known functions of mTOR include the following ([Bjornsti and Houghton 2004](#)):

- mTOR functions as a sensor of mitogens, growth factors and energy and nutrient levels;
- Facilitating cell-cycle progression from G1-S phase in appropriate growth conditions;
- The PI3K/mTOR pathway itself is frequently dysregulated in many human cancers, and oncogenic transformation may sensitize tumor cells to mTOR inhibitors;
- The mTOR pathway is involved in the production of pro-angiogenic factors (i.e., VEGF) and inhibition of endothelial cell growth and proliferation;
- Through inactivating eukaryotic initiation factor 4E binding proteins and activating the 40S ribosomal S6 kinases (i.e., p70S6K1), mTOR regulates protein translation, including

the HIF-1 proteins. Inhibition of mTOR is expected to lead to decreased expression of HIF-1.

### **1.2.1.1 Non-clinical experience**

For latest information on the pre-clinical pharmacology and toxicology of everolimus, please refer to the current Investigator's Brochure (IB).

### **1.2.1.2 Clinical experience**

In oncology, everolimus has been in clinical development since 2002 for patients with various hematologic and non-hematologic malignancies; as a single agent or in combination with antitumor agents. Malignancies that are currently being evaluated in Novartis sponsored studies include the following: metastatic renal cell carcinoma, breast cancer, pancreatic neuroendocrine tumors (pNET/NET), diffuse large B cell lymphoma, and hepatocellular cancer. In addition, treatment of patients with TSC associated subependymal giant cell astrocytoma (SEGA), renal angiomyolipoma, and epilepsy are also being evaluated.

Phase I dose escalating studies, exploratory Phase I/II/III studies with everolimus as single agent or in combination with other anti-cancer agents, Phase II/III studies of everolimus in different indications, Phase III double-blind studies and Phase IV studies are contributing to the extensive clinical database.

Approximately 27,399 patients, (excluding those patients who received marketed Afinitor®/Votubia®, those on roll over studies as well as excluding investigator-sponsored studies) have been enrolled in studies with everolimus as of 31-Mar-2015.

## **Oncology**

Everolimus was approved by FDA on 30-Mar-2009 under the trade name Afinitor® for the treatment of patients with advanced RCC after failure of treatment with sunitinib or sorafenib. The European Commission (EC) approved Afinitor® on 03-Aug-2009 for the treatment of patients with advanced RCC, whose disease has progressed on or after treatment with vascular endothelial growth factor (VEGF)-targeted therapy. As of 31-Mar-2015, Afinitor® has been approved in 121 countries worldwide including Japan for the treatment of patients with advanced RCC.

On 05-May-2011, FDA approved Afinitor® for the “treatment of progressive pNET in patients with unresectable, locally advanced or metastatic disease. Afinitor is not indicated for the treatment of patients with functional carcinoid tumors”. The EC approved Afinitor® on 24-Aug-2011 for the treatment of unresectable or metastatic, well- or moderately-differentiated neuroendocrine tumors of pancreatic origin in adults with progressive disease. As of 31-Mar-2015, Afinitor® has been approved in >115 countries worldwide for the treatment of patients with pNET/neuroendocrine tumors. In Japan, Afinitor was approved in pNET in 2011 and approved in NET in 2016 based on the additional results from the study for patients with GI or lung NET.

On 20-Jul-2012, FDA approved Afinitor® for the treatment of postmenopausal women with advanced hormone receptor-positive, HER2-negative breast cancer in combination with exemestane, after failure of treatment with letrozole or anastrozole. The EC approved Afinitor®

on 23-Jul-2012 for the treatment of hormone receptor-positive, HER2/neu negative advanced breast cancer, in combination with exemestane, in postmenopausal women without symptomatic visceral disease after recurrence or progression following a non-steroidal aromatase inhibitor. As of 31-Mar-2015, Afinitor® has been approved in >115 countries including Japan for the treatment of patients with advanced hormone receptor-positive, HER2-negative breast cancer.

### **Tuberous sclerosis complex**

Afinitor® received accelerated approval from FDA on 29-Oct-2010 for the “treatment of patients with SEGA associated with tuberous sclerosis complex (TSC) who require therapeutic intervention but are not candidates for curative surgical resection. The EC granted conditional approval on 02-Sep-2011 for everolimus under the trade name Votubia® for the “treatment of patients aged 3 years and older with SEGA associated with TSC who require therapeutic intervention but are not amenable to surgery. Afinitor® received accelerated approval from FDA on 26-Apr-2012 for the “treatment of adult patients with renal angiomyolipoma and TSC, not requiring immediate surgery

In Japan, Afinitor® was approved for adult patients with SEGA associated with TSC as well as AML associated with TSC.

For further details please refer to the current everolimus IB.

### **Pharmacokinetics**

Everolimus is rapidly absorbed after oral administration, with a time to reach the maximum drug blood concentration ( $t_{max}$ ) of 1-2 hours postdose. The extent of absorption is estimated at above 11%. The area under the blood concentration-time curve (AUC) is dose-proportional over the dose range of 5 to 70 mg tested while maximum drug blood concentration ( $C_{max}$ ) appears to plateau at dose levels higher than 20 mg. The terminal half-life in cancer patients averaged 30 hours, which is similar to that in healthy subjects. A high-fat meal altered the absorption of everolimus with 1.3 hour delay in  $t_{max}$ , a 60% reduction in  $C_{max}$  and a 16% reduction in AUC. In whole blood, approximately 80% of everolimus is contained in red blood cells. Of the fraction of drug contained in plasma, 74% is protein-bound. The apparent distribution volume ( $V_z/F$ ) after a single dose was 4.7 L/kg. Everolimus is eliminated by metabolism, mainly by hydroxylation, then excreted into the feces >80%.

Everolimus is mainly metabolized by CYP3A4 in the liver and to some extent in the intestinal wall. Everolimus is also a substrate of P-glycoprotein (PgP). Therefore, absorption and subsequent elimination of systematically absorbed everolimus may be influenced by medicinal products that interact with CYP3A4 and/or P-glycoprotein. In vitro studies showed that everolimus is a competitive inhibitor of CYP3A4 and of CYP2D6 substrates, potentially increasing the concentrations of medicinal products eliminated by these enzymes. In two phase III clinical trials in patients following kidney transplantation, strong inhibitors of CYP3A4 (azoles, antifungals, cyclosporine, erythromycin) have been shown to reduce the clearance of everolimus therapy thereby increasing everolimus blood levels. Similarly, Rifampin, a strong inducer of CYP3A4, increases the clearance of everolimus thereby reducing everolimus blood levels. Another drug-drug interaction study of everolimus administered with a sensitive CYP3A4 substrate midazolam showed that while everolimus did not influence the hepatic

metabolism of midazolam, it led to minor increases in bioavailability of midazolam likely due to influences of pre-systemic metabolism. Caution should be exercised when co-administering everolimus with CYP3A4 inhibitors, inducers, or substrates with a narrow therapeutic index.

## **Pharmacodynamic studies**

Pharmacokinetic/pharmacodynamic modeling based on inhibition in a peripheral biomarker (S6 kinase inhibition in peripheral blood mononuclear cells) suggests that 5 to 10 mg daily should be an adequate dose to produce a high-degree of sustained target inhibition. Furthermore, molecular pharmacodynamic (MPD) studies using IHC in biopsied tumor tissue assessed the degree of inhibition and its duration (for p-S6, p-4E-BP1 and p-Akt expression) with the daily and weekly dosing. The pathologist was blinded for the biopsy sequence. There was almost complete inhibition of p-S6 at all doses and schedules studied ( $p=0.001$ ). Preliminary results suggest a dose-related decrease in p-4E-BP1 and increase in p-Akt expression with maximal effect at 10 mg daily and  $\geq 50$  mg weekly.

For further details please refer to the current everolimus IB.

## **2 Rationale**

### **2.1 Study rationale and purpose**

The purpose of this study is to collect and assess long-term safety of everolimus in patients who are currently receiving everolimus treatment in a Novartis-sponsored study that has reached its study objectives, are not progressing on the current study treatment as defined by the parent protocol and are unable to access everolimus treatment outside of a clinical study. Parent studies eligible to participate in the roll-over study will be decided by Novartis. Investigator initiated trials (IITs) will not be included. The primary objective of the parent study must have been reached and the parent study must be in the process of being completed and reported.

Patients will continue to receive everolimus until one of the following occurs: no treatment benefit (disease progression) as defined in the parent protocol, unacceptable toxicity develops, consent withdrawal, protocol non-compliance, the investigator feels it is no longer in the patient's best interest to continue therapy, or the patient's death.

### **2.2 Rationale for the study design**

This is a multi-center, open-label, phase II study to collect and assess long-term safety of everolimus for patients being treated in a current Novartis-sponsored study and who are benefiting from treatment with everolimus.

The study will not include a screening phase as patients will transfer directly from the parent studies and will commence treatment with everolimus as soon as they are consented and meet the inclusion criteria of this roll-over study protocol.

### **2.3 Rationale for dose and regimen selection**

The selected doses and regimen will be based on the dose ranges and regimen available in the parent studies. Everolimus will be provided as 2.5 or 5 mg tablets to be administered using every day. See more details in [Section 6.1.1](#).

## 2.4 Rationale for choice of combination drugs

Patients may be allowed to continue combination with everolimus in combination with other therapies if they are currently receiving the therapies on the parent protocol and are driving benefit judged by the investigator.

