## 6 Treatment

### 6.1 Study treatment

For study treatment refer to everolimus plus combination drugs used in the parent study and for investigational treatment refer to everolimus.

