#### **6.4.3 Prohibited concomitant therapy**

Treatment with systemic anticancer agents (chemotherapy, hormone therapy, targeted or biologic agents) other than everolimus is not permitted until disease progression is documented and everolimus is permanently discontinued.

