### **6.6 Study drug preparation and dispensation**

The investigator or responsible site personnel must instruct the patient or caregiver to take the study drugs as per protocol. Study drug(s) will be dispensed to the patient by authorized site personnel only. All everolimus dosages prescribed to the patient and all dose changes during the study must be recorded on the Everolimus Dosage Administration Record eCRF.

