1.1.4 Treatments (study treatment, concomitant therapies, compliance)

Exposure to everolimus will be summarized for FAS and will be based only on dose administered within this protocol. Study treatment administered during the parent study will not be taken into account.

The following algorithm will be used to calculate the duration of exposure in days:

- Duration of exposure to everolimus (days) = (date of last administration of everolimus) – (date of first administration of everolimus) + 1.

The date of first administration of everolimus is derived as the first date when a nonzero dose of everolimus was administered and recorded on the database of this protocol. The date of last administration of everolimus is defined as is the last date when a nonzero dose of study drug was administered and recorded on the database of this protocol.

The duration of exposure in years is calculated by dividing the duration of exposure in days by 365.25.

The duration includes the periods of temporary interruption.

Everolimus dose administration will be listed by patient.

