1.2 Safety evaluation

For all safety analyses, the safety set will be used.

The overall observation period will be divided into two mutually exclusive segments:

1. on-treatment period: from day of first dose of study medication to 30 days after last dose of study medication
2. post-treatment period: starting at day 30 after last dose of study medication.

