1.2.1 Adverse events (AEs)

Summary tables for AEs have to include only AEs that started or worsened during the on-treatment period, the **treatment-emergent** AEs. However, all safety data (including those from the post-treatment periods) will be listed and those collected during the post-treatment period are to be flagged.

The incidence of all treatment-emergent AEs (number and percentage) will be summarized by system organ class (SOC), preferred term, and maximum severity, relation to study treatment.

Deaths reportable as SAEs and non-fatal serious AEs will be listed by patient.

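### If parent-study partner drugs continue, the planned AE tables do not separate everolimus alone from everolimus in combination, and the protocol sections on partner drugs conflict

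*Protocol*

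**What the plan says.** **Which drugs may be given.** Protocol 2.4: "Patients may be allowed to continue combination with everolimus in combination with other therapies", provided the patient already receives them on the parent protocol and the investigator sees benefit. Protocol 6.1 defines the terms accordingly: "For study treatment refer to everolimus plus combination drugs used in the parent study and for investigational treatment refer to everolimus". Protocol 6.1.6 refers sites to the parent protocol and package insert for other study treatment, and Protocol 8.2.2 provides for more than one study treatment when the causality of a serious AE (SAE) is assessed. Protocol 6.4.3 points the other way. Treatment with systemic anticancer agents, hormone therapy included, "other than everolimus is not permitted until disease progression is documented and everolimus is permanently discontinued".

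**What is recorded and reported on dosing.** Protocol 6.6: "All everolimus dosages prescribed to the patient and all dose changes during the study must be recorded on the Everolimus Dosage Administration Record eCRF". SAP 1.1.4: "Exposure to everolimus will be summarized for FAS and will be based only on dose administered within this protocol", and "Everolimus dose administration will be listed by patient". Protocol 10.3 has the same listing. Protocol 6.6.3.3, on handling of other study treatment, is marked not applicable.

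**How AEs are summarised.** SAP 1.2 uses the Safety Set for all safety analyses, and its only grouping is by time: "The overall observation period will be divided into two mutually exclusive segments", namely on-treatment and post-treatment. SAP 1.2.1: "The incidence of all treatment-emergent AEs (number and percentage) will be summarized by system organ class (SOC), preferred term, and maximum severity", together with relation to study treatment. Protocol 8.1.1 asks for that relation as a single yes or no. The parent study is recorded for each patient (Protocol 6.5.1 and 7.1.1.3) and summarised with demographics (SAP 1.1.3), but it is not crossed with AEs.

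**The concern.** The trial has one objective, the long-term safety of everolimus, and one endpoint, the frequency and nature of AEs (Protocol Table 3-1). If some patients take everolimus alone and others take it with a partner drug that has its own toxicity, each percentage in the AE tables averages over two regimens in a proportion that the planned output does not show. A reader who takes the percentage as the frequency on everolimus could be misled in either direction.

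The relatedness table does not resolve this. Under Protocol 6.1, study treatment includes the partner drug, so a non-serious AE caused by the partner alone is still correctly marked as related.

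**Working it through.** The plan states no figure on this point (no sample size, expected incidence or share on combination), so there is nothing to reproduce. The check is to trace the text and then bound what a pooled table can tell.

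**Step 1: can two regimens occur?** Protocol 2.4, 6.1, 6.1.6 and 8.2.2 all provide for partner drugs. The background in Protocol 1.2.1.2 describes development both as a single agent and in combination, and names an approved combination with exemestane in breast cancer. Protocol 6.4.3 would exclude systemic anticancer partners. The documents do not say which section prevails, or which parent studies feed the roll-over. The share on combination may be zero or substantial.

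**Step 2: does any planned output separate the regimens?**
- Grouping (Protocol 10.4.1, SAP 1.2): by time segment only.
- AE tables (SAP 1.2.1): by system organ class, preferred term, maximum severity and relation; not by regimen or parent study.
- Exposure and dose outputs (SAP 1.1.4, Protocol 10.3): everolimus only.
- Causality: one answer for study treatment as a whole (Protocol 8.1.1). Causality by drug exists for SAEs only (Protocol 8.2.2), and no table of it is planned.

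No planned output separates them.

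**Step 3: what does a pooled incidence say about everolimus alone?** Let w be the share of the Safety Set on combination, P the pooled incidence of an AE, and a and c the incidences on everolimus alone and in combination.

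P = (1 − w)·a + w·c, so P − a = w·(c − a).

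The gap is zero when w = 0, and its sign is the sign of c − a. Solving for a with c anywhere between 0 and 1:

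max(0, (P − w)/(1 − w)) ≤ a ≤ min(1, P/(1 − w)).

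For P = 0.30 and w = 0.20, the lower limit is (0.30 − 0.20)/0.80 = 0.125 and the upper limit is 0.30/0.80 = 0.375. Other values, all assumed because the documents give neither P nor w:

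| Pooled P | w = 0 | w = 20% | w = 50% | w = 80% |
|---|---|---|---|---|
| 10% | 10% | 0–12.5% | 0–20% | 0–50% |
| 30% | 30% | 12.5–37.5% | 0–60% | 0–100% |
| 50% | 50% | 37.5–62.5% | 0–100% | 0–100% |

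These are logical limits, not likely values. They show that the pooled figure pins down the everolimus-alone figure only when w is near zero.

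**Step 4: direction.** With assumed values a = 10% and c = 30%, the pooled figure is 10% + w·20%: 12%, 16% and 20% for w = 10%, 30% and 50%. With a = 30% and c = 10% it is 30% − w·20%: 28%, 24% and 20%. The documents contain nothing to choose between the two.

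**The case against.** The strongest reply is that the problem may not exist. If Protocol 6.4.3 governs, few or no patients have a partner drug, w is near zero and the pooled table is adequate. That stands as a possibility, and it is why the sections have to be reconciled first. It does not dispose of the point, because two sections as written allow partner drugs and the planned output would not show whether any were used.

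A second reply is that no objective asks for AE frequency on monotherapy. The study is descriptive, spans several parent studies and has no comparator, so the pooled percentage validly describes the patients enrolled. This also stands. The split is therefore an improvement in interpretation and not the repair of an invalid analysis.

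A reader might also infer three stronger things that the documents do not support:
- *That partner drugs are not captured at all.* The text that can be read describes only an everolimus dosing record, but the body of Table 7-1, which marks what enters the database, is not readable here. A concomitant-medication or partner-drug page cannot be excluded.
- *That the regimens could never be separated after database lock.* The parent study and the parent-study subject number are recorded for each patient. Because Protocol 2.4 limits combinations to therapies received on the parent protocol, a patient from an everolimus-only parent study cannot belong to its combination group. For combination parent studies the proxy is imperfect, since continuing is optional and no partner stop date is described. SAE causality is also recorded by drug. The separation is unplanned, not impossible.
- *That the tables overstate AE frequency on everolimus by some factor.* Any such factor comes from assumed incidences and an assumed share. Nor does either document specify table columns: the pooling is inferred from the absence of any regimen grouping.

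**Conclusion.** The point holds as a gap in the planned analysis and an internal conflict in the protocol. Protocol 2.4 and 6.1 must be reconciled with 6.4.3. As far as partner drugs are continued, the planned AE summaries mix everolimus alone with combination use, and neither the exposure outputs nor the single causality answer for non-serious AEs separates them. The pooled incidence need not equal the incidence on everolimus alone. The size and direction of the difference cannot be derived from the documents, and it is zero if nobody continues a partner drug.

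The conclusion rests on two readings: that the absence of a regimen grouping in SAP 1.2 and 1.2.1 means none is planned, and that at least some patients may enter on a combination. The SAP supplied (version 1.0, 20-Apr-2015) is older than Protocol Amendment 01 (30-Aug-2016), which clarified the definition of study treatment, so the SAP merits a check against the current definition in any case. This is a cheap improvement; it does not invalidate the total figures.

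**What to change.** 1. Reconcile Protocol 2.4, 6.1 and 6.4.3, so that it is clear whether and which partner drugs may continue.
2. In SAP 1.2.1, present AE incidence in three columns: everolimus alone, everolimus in combination, and total. Group by status at roll-over, so that each patient stays in one column.
3. In SAP 1.1.4, list the partner drug and its stop date beside the everolimus dose listing. The stop date does not alter the columns; it lets a reader see which AEs began after the partner drug had ended.
4. Check whether the eCRF already captures the partner drug with start and stop dates. If not, add that item. If it cannot be added, use the parent-study regimen, identifiable from the recorded parent study number, as a proxy and say so. Under Protocol 2.4 the proxy's main error is to place patients who have dropped their partner drug in the combination column.

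The cost is two extra table columns, one listing field and possibly one eCRF item. The downside is thin cells if few patients are on combination. The total column is kept, so nothing now planned is lost. If no patient is on combination, the output will document that.
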